In Kenya, Jhpiego has instituted a policy of electronic compensation for study participants, with the aim of minimizing the risk of carrying money while in the field for the purpose of reimbursing participants. This system uses mobile electronic money transfer (M-PESA) as an alternative to the cash advance system. To receive reimbursement, the system collects each participant’s name, phone number, national identification number, and thumbprint. During reimbursement the registered participant is asked to place their thumb on the biometric reader, this information is sent to the Jhpiego Nairobi finance servers, and this is reviewed against the budgeted amount, and the money released through Mpesa into the participants Mpesa account. The finance department will retain these digital records indefinitely for future audit. This information will not be used for any other purpose other than audits. In addition it will not be accessible to the research team or any other person after the research activity. Security measures are maintained to protect the data stored on the Jhpiego servers.

X. Study Management

A. Oversight Plan:

1. Describe how the study will be managed.

The study will be managed by a multi-disciplinary team of OB/GYNs, clinicians, public health practitioners and expert researchers based in the U.S. and Kenya. The PI for the study, [name], will be responsible for overseeing the activities and research staff and ensuring compliance with approved study protocols and practices. The PI will work

closely with co-investigators to facilitate trainings of data collectors and providers in the paper partograph and ePartogram group, oversee partograph review, research ethics, and ensure data quality and confidentiality.

To ensure study activities are carried out ethically and within the allotted study period, the PI and co-investigators will carry out roles as outlined below:

Table 8. Management plan:

Role	Responsibilities
Study Manager (co-investigator)	
 Provide day-to-day management and oversight for study implementation at facilities Conduct site orientations and stockups Oversee research team and data collection, and liaise with study sites Conduct qualitative interviews Share weekly progress updates and facilitate bi-weekly study team calls during data collection

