While study results demonstrated many benefits of ePartogram use, additional needed software refinements were identified, and further research is needed to assess its use in a greater variety of clinical settings. The proposed ePartogram effectiveness aims to further test the ePartogram software and use of ePartogram on clinical decision-making and care.

[figure not shown]
III. Study Design

- A. Provide an overview of your **study design and methods**.

Study Design

The study design is a quasi-experimental design evaluation with labor management outcomes compared for the study period between two study groups, intervention and control. The study will involve mixed methods – quantitative and qualitative data. The study is depicted below.

Figure 1. Study Design and Phases

Methods

The study will be conducted in the following phases.

Phases

- 1) An initial group of **facilities selected** for participation will be confirmed in Kisumu County and Meru County. A rapid formative assessment of possible facilities collected data on:
 - a. training needs on the paper partograph and
 - b. supplies, drugs and equipment available in stock for monitoring of normal labor, management of complications and referrals (facility assessment tool; this will be repeated every 3 months) (?).
 - c. percent of births recorded in the register at the facility in past 3 months that had a partograph started and used.
 - d. this activity received a non-HSR determination.
- 2) In each region, we expect approximately 6 facilities to participate. Within each region, equal numbers of facilities that will be purposively assigned to the study groups. Each study group will have facilities that have a similar birth volume, staffing levels, and BEmONC/CEmONC status, as much as possible so the two group are similar
 - a. Kisumu District Hospital and Meru Teaching and Referral Hospital must be intervention sites and will not be randomly allocated to the study group.
- 3) We will seek **approvals**:
 - a. 2 IRB approvals (JHSPH and KEMRI in Kenya) (see section X.E of this document).
 - b. Ministry of Health Approval to work in their sites
 - c. County Approvals (Kisumu and Meru)
 - d. Facility in-charge agreement will be sought at time of provider enrollment.
- 4) A similar three-day **whole-site training** will be carried out in each participating health facility in both study groups on labor management and partograph use by providers following Kenyan and WHO guidelines.

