In the exercise of completing the Health Worker Line Listing at each facility, we will document the numbers of cadres (Kenya Enrolled Community Health Nurses; Kenya Registered Community Health Nurses; Kenya Registered Nurses; Kenya Registered Nurse Midwives and Bachelor of Science in Nursing Nurses) and doctors (ObGyn and medical officers). A purposive sample of all cadres using the ePartogram or partograph will be selected. At high-volume sites, a sample of half of the providers on duty in a month and half of the supervisors will be interviewed. At lower-volume sites: all providers and supervisors will be interviewed. We will also interview each facility in-charge and district authority. So there are 4 respondent types: providers, supervisors, facility-in-charge and district authority.

The study staff will carry out the interviews when visiting the facility starting in second month. Each facility will have qualitative data collected at one point in time.

For the qualitative data, we will select 8 busy facilities: assume 2 to 8 providers per site (average 4 providers), $8*4 = 32$. One supervisor from each site: 8. Up to 4 in-charges and 4 district authorities. **Total 48 participants**. Note these qualitative participants will be part of the larger group of participants who consent to be part of the in the overall study.

IV. Participants

Describe the study participants and the population from which they will be drawn. Specify the inclusion and exclusion criteria. If you plan to include children, note their ages and whether you will include children in foster care. Note if the participants are particularly vulnerable in terms of cognitive limitations, education, legal migration status, incarceration, poverty, or some combination of factors.

Facilities

The facilities will include the higher referral-level hospitals in Kisumu and Meru, as well as lower level hospitals. The facilities will include both BEmONC and CEmONC sites.

Facility Inclusion Criteria:

- In Kisumu or Meru
- BEmONC or CEmONC sites
- At least one SBA on duty in labor ward 24 hours per day
- Facility in-charge or in-charge of L&D ward available physically or remotely 24 hours per day
- Use WHO modified paper partograph
- Adequate supply of paper partographs and maternity registers
- Availability of reliable transportation for referrals (e.g. functional ambulance or other) 24 hours per day

Facility Exclusion Criteria:

- Facility not registered with MOH

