Intrapartum death (fresh stillbirth rate) (Tool 5)	Number of fresh stillbirths. This is a count variable.	All live births	Same as above.
Adverse perinatal events (Neonatal deaths <24 hours+ intrapartum death (fresh stillbirth rate))	Number of neonatal deaths and fresh stillbirths	All live births	Same as above.

Statistical analysis plan

Outcomes will be dichotomous, yes/no for each measure.

In the main statistical analysis of our primary outcomes, we will focus on program effect (intervention (ePartogram) group of facilities versus comparison (paper program) group of facilities) as the main predictor of interest. The analysis will be performed at the level of the individual case (partogram). In preliminary analyses we will conduct univariable and bivariable analyses to assess the distribution of key variables and joint distributions and unadjusted relationships.

In final analyses addressing study aims, we will fit multi-level, multivariable regressions models for the outcomes with adjustment for possible confounders and account for clustering by provider and/or study clinic by the use of GEE.

While we have selected clinics roughly matched between the intervention and comparison regions, we will still evaluate confounding to attain the least biased estimate of our intervention effect. Facility level possible confounders are: monthly case load of laboring women, number of providers, key equipment availability etc. Provider-level possible confounders that may be adjusted for are years of work experience since graduation and cadre. Woman-level possible confounders are age and parity.

5. Describe whether you are collecting or storing **personal identifiers**, and if yes, why you need them, and when and how you plan to dispose of them. Signatures on consent forms are considered to be identifiers.

Identifiers of Providers

Our study will assign each facility and each provider a study id number of the Health Worker Line Listing form to be updated monthly. This will be kept separately from partograph data.

partograph review analysis: the paper partograph has a place for a provider to sign it. When we scan/photocopy paper partographs, we will obscure the provider name (cover with lose paper) but will we add/write on it the provider study id number.

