a. If the study has **different arms**, explain the process for **assigning participants** (intervention/control, case/control), including the sequence and timing of the assignment.

This will be a cluster-randomized trial. See section on randomization under Section III Methods.

b. If human biospecimens (blood, urine, saliva, etc.) will be collected, provide details about who will collect the specimen, the volume (ml) and frequency of collection, how the specimen will be used, stored, identified, and disposed of when the study is over. If specimens will be collected for use in future research (beyond this study), complete the Biospecimen Repository section below. **N/A**

c. If genetic/genomic analyses are planned, address whether the data will be contributed to a GWAS or other large dataset. Address returning unanticipated incidental genetic findings to study participants. **N/A**

d. If clinical or laboratory work will be performed at JHU/JHH, provide the JH Biosafety Registration Number. **N/A**

e. If you will perform investigational or standard diagnostic laboratory tests using human samples or data, clarify whether the tests are validated and/or the lab is certified (for example is CLIA certified in the U.S.). Explain the failure rate and under what circumstances you will repeat a test. For all human testing (biomedical, psychological, educational, etc.), clarify your plans for reporting test results to participants and/or to their families or clinicians. Address returning unanticipated incidental findings to study participants. **N/A**

f. If your study involves medical, pharmaceutical or other therapeutic intervention, provide the following information:

- Will the study staff be **blind** to participant intervention status?

The in-charge and the providers at selected ePartogram sites will know that their site has been selected to use this innovation, so they will not be blinded.

The in-charge and providers at the paper-partograph control sites will not be told officially about the ePartogram being used in other sites, just that their site is part of a partograph training and monitoring intervention. These individuals may find out about the ePartogram being used elsewhere, from contamination/spillover from providers in other sites or from communications with county health officials.

- Will participants receive standard care or have current therapy **stopped**?

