Services will be provided to clients as part of routine MOH service provision. No adverse events as a result of this study are anticipated. If complications arise during routine service provision, the regular mechanisms will be followed, such as contacting senior providers and initiating referrals.

2. If a Data Safety Monitoring Board (DSMB), or equivalent will be established, describe the following:
 - a. The DSMB membership, affiliation and expertise.
 - b. The charge or charter to the DSMB.
 - c. Plans for providing DSMB reports to the IRB.
3. Describe plans for interim analysis and stopping rules, if any.

D. Reporting unanticipated problems/adverse events (AE's) to the IRB (*all studies must complete this section*):

Describe your plan for reporting to the IRB and (if applicable) to the sponsor. Include your plan for government-mandated reporting of abuse or illegal activity.

NOTE: The IRB does not require submission for all AEs, only those that are unanticipated, pose risk of harm to participants or others, and are related to the study.

ADVERSE EVENTS EXPECTED & UNEXPECTED

- At baseline, study staff (or a designated provider onsite) will visit the study sites to scan registers for the three previous months to establish the baseline rate for maternal and early newborn deaths and fresh stillbirths. . .
- Every 2 weeks, the study team will obtain the maternity register scan from each facility. We will determine the number of deliveries, number of live births, and the number of maternal and early newborn deaths and fresh stillbirths. We will determine the appropriate rates and whether any are more than 10% above the expected/normal rate.
- A summary log will be created for recording the number of deliveries, births, and adverse maternal or newborn outcomes for each 2 week period. This log will have the woman's facility admission number id on it obtained from the register. If this log indicates that normal levels have occurred, this summary AE log will be submitted to IRB along with progress report.
- If the normal level is exceeded (>10% higher than the average monthly total from 3 months prior to the intervention), Jhpiego will prepare a severe adverse events (SAE) report and the SAE policy will take effect with expedited reporting to IRB.

REPORTING

- If any unanticipated problems or adverse events occur, the study team will follow JHSPH IRB policy no. 103.06, "Reports of Unanticipated Problems Involving Risks to Participants or to Others".

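### P1–P3 have no visible pre-training measurement although facilities are assigned purposively, so a systematic pre-existing charting gap between arms is only partly controlled

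*Combined protocol and SAP*

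**What the plan says.** Section III.A describes a quasi-experimental study with "labor management outcomes compared for the study period between two study groups, intervention and control". Within each region there are "equal numbers of facilities that will be purposively assigned to the study groups", and one named hospital in each of the two counties "must be intervention sites and will not be randomly allocated to the study group". Groups are to be made as alike as possible on births, staffing and emergency obstetric care level. Section V.C.6.a nevertheless states "This will be a cluster-randomized trial" and points to a randomization text in Section III that is not there.

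Three sources of pre-study information are visible. The formative assessment covers training needs, supplies and, as item 1c, the "percent of births recorded in the register at the facility in past 3 months that had a partograph started and used". At baseline, staff or an onsite provider will "scan registers for the three previous months to establish the baseline rate for maternal and early newborn deaths and fresh stillbirths" (Section X.D). That serves adverse-event monitoring and relates to S1, not to P1–P3.

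On adjustment, the statistical analysis plan in Section V.C.4 says "Facility level possible confounders are: monthly case load of laboring women, number of providers, key equipment availability etc". Table 5 adds facility type, client volume, region and provider variables as possible controls. The same section also lists cadre and experience at provider level, and age and parity at woman level.

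**The concern.** When facilities are chosen for an arm rather than randomized, the arms may already differ in how well labor is charted and acted upon. A comparison made only after training carries such a difference into the estimated effect. Case load, staffing and equipment do not measure charting quality, and neither does coverage: the Kenyan survey cited in Section II found the partograph used in 88% of cases but all components completed in only 58%.

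The same survey illustrates what is at stake for P3. It reports appropriate action in 78% of cases that reached the action line. The sample size treats the control level as unknown, sets it at 50%, and expects 80% with the ePartogram. The definitions are not identical. Even so, an ePartogram arm observed at 80% would sit close to a level already reported in Kenya, and no pre-training figure would show whether that arm had moved. The study is meant to advise the Ministry of Health on wider use, so the attribution matters.

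**Working it through.** **The plan's own figure.** Inputs from Section III.B and Table 1: 50% versus 80%; ICC 0.15; coefficient of variation 90%; 671 births per month in 6 facilities, 80% with a partograph, 19% complicated. Alpha and power are not stated; two-sided 0.05 and 80% are inferred because they reproduce the table.

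- Unadjusted n = (1.96 + 0.84)² × (0.5×0.5 + 0.8×0.2) / 0.30² = 35.8 (plan: 36).
- Cluster size = 671 × 0.80 × 0.19 / 6 = 17.0.
- Design effect = 1 + (17.0 − 1) × (1 + 0.9²) × 0.15 = 5.34 (plan: 5.3).
- 35.76 × 5.344 = 191 complicated labors; 191 / 0.19 ≈ 1006 partographs per arm (plan: 1004).

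**Chance gap.** At a 50% level the SD of true facility rates is √(0.15 × 0.5 × 0.5) = 0.194. The SE of a 6-versus-6 difference is 0.194 × √(2/6) = 0.112, so the 95% range is ±1.96 × 0.112 = ±22 points. For ICC 0.05 to 0.20 it is ±13 to ±25 points. This is the variation that the design effect and the GEE clustering are there to cover.

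**Systematic gap.** Take 191 / 6 = 31.8 complicated labors per facility, equal facility sizes, and a comparison of facility means. The SE for P3 is √[0.25 × (0.15 + 0.85/31.8) × 2/6] = 0.121. Suppose the ePartogram has no effect but the arms differ by a fixed amount from the start. The documents give no value for this gap, so 10, 20 and 30 points are assumptions. The probability of a significant result is then:

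| Outcome, ICC | SE | 10 points | 20 points | 30 points |
|---|---|---|---|---|
| P3, 0.15, normal test | 0.121 | 13% | 38% | 70% |
| P3, 0.15, t with 10 df | 0.121 | 12% | 32% | 61% |
| P3, 0.05, normal test | 0.082 | 23% | 69% | 96% |
| P1, 0.15, normal test | 0.114 | 14% | 42% | 75% |

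The P1 row uses 1004 / 6 = 167 charts per facility and borrows the ICC and 50% level that the plan sets for P3.

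**What 20 old charts per facility would give.** At ICC 0.15 the reliability of a 20-chart facility proportion is 20 × 0.15 / (1 + 19 × 0.15) = 0.78, which is usable for P1. If the before–after facility correlation were 0.6 to 0.8 (an assumption that common training could weaken), adjustment would remove 0.78 × 0.6² = 28% to 0.78 × 0.8² = 50% of the between-facility variance. For P3, 20 × 0.19 is about 4 complicated labors per facility, too few to use. The action fields also come from a stamp introduced for this study (Table 4, tool 3), so they are absent from older charts.

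**The case against.** The plan has real safeguards: equal allocation within region, matching, the same three-day training and stocking of supplies in both arms, and adjustment for facility type, region, provider and woman variables. The confounder list is open-ended, so item 1c is not excluded. A concurrent comparison without a baseline is also openly declared. All of this stands. A reader might infer that the study cannot separate the ePartogram effect from prior differences at all; the documents do not support that, because these measures give partial protection.

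A reader might also set the ±22 points against the expected 30-point effect and call it bias. It is not: it is chance spread, and the design effect is the plan's allowance for it. Nor does the ICC of 0.15 amount to an admission that charting habits differ. Section III.B justifies it by the mix of facility types, part of which adjustment for facility type may absorb.

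The remedy has limits too. The statement that partographs stay at the facility concerns study charts, so retrieval of older ones is unconfirmed. The baseline register scan need not involve a staff visit. The formative assessment covered candidate sites under a non-human-subjects-research determination. Section II itself warns that charts are often filled in afterwards for the record, so old charts may show recording rather than monitoring.

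None of this supplies a pre-training value of P1–P3, or a covariate that measures earlier charting quality.

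**Conclusion.** The point holds as a limitation that should be reduced, not as a fatal flaw. No visible phase, tool, timeline row or analysis measures P1–P3 before training in either arm, and the one pre-study measure of partograph use is not named for adjustment. Figure 1 and part of Section X are not in the available text, hence the word visible.

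The uncovered risk is a systematic gap from purposive assignment. Its size is unknown, and nothing in the documents shows that one exists. If one does, a gap of 10 to 30 points would produce a significant P3 result with no true effect in about 13% to 70% of studies (12% to 61% with t on 10 df), instead of the nominal 5%. This rests on ICC 0.15, a 50% level, equal facility sizes and incomplete control of the gap by the planned covariates. A smaller ICC makes the false-positive rate higher.

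**What to change.** 1. Pre-specify item 1c, by facility, as a covariate in the P1–P3 models, or at least as a sensitivity adjustment. Confirm first that it exists for all 12 final sites and may be used for research. State that coverage is a crude proxy for completeness.
2. Where pre-training charts can be retrieved, scan a fixed consecutive set in both arms, for example 20 per facility. The inclusion criterion "Use WHO modified paper partograph" means the form should already be in use everywhere. Extract them with Tool 4. Use each facility's baseline P1 proportion as a balance check and as the covariate for P1, replacing item 1c if degrees of freedom are short.
3. State that P2 and P3 actions have no baseline because the stamp is new, and carry that limit into the conclusions.
4. Reconcile the cluster-randomized label in Section V.C.6.a with the purposive assignment in Section III.A.

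Cost: item 1c is one model term on data already collected at candidate sites. The chart sample is 12 × 20 = 240 extractions, 240 / 2,200 = 11% more work for the planned partograph reviewers. It also needs an IRB amendment that covers charts completed before provider consent. Each facility-level covariate uses one degree of freedom out of 12 facilities.

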P2. Decision-making and actions taken to maintain normal labor (Tool 4)	Data on each partograph parameter will be entered for each time period, as well as actions taken in labor. Jhpiego clinical rules will be applied to the data in the extraction database to determine appropriate clinical actions for a labor without any complication. This is a binary variable.	Labors in which Section 3 marked as “Normal Labor”	First, we will examine the frequency/prevalence of each clinical action taken in normal labor and compare between the two study groups. Second, we will carry out same analysis as for Objective P1.
P3. Detection, decision-making and action to address deviations from normal labor and complications arising during labor—for ‘slow’ labor, prolonged labor, obstructed labor and cephalo-pelvic disproportion	Data on each partograph parameter will be entered for each time period, as well as actions taken in labor. Jhpiego clinical rules will be applied to the data in the extraction database to determine appropriate clinical actions for a labor with a specific complication. This is a binary variable.	Labors in which Section 3 marked “Slow labor, prolonged labor, obstructed labor or cephalo-pelvic disproportion”	First, we will examine the frequency/prevalence of each clinical action taken in selected complications and compare between the two study groups. Second, we will carry out same analysis as for Objective P1.
-- for all complications (Tool 4)	Same as above. A composite variable will be created for all complications. This is a binary variable.	Labors in which Section 3 marked as ANY complication	First, we will examine the frequency/prevalence of each clinical action taken in all

			complications and compare between the two study groups. Second, we will carry out same analysis as for Objective P1.
S1. Is facility use of ePartogram (vs. paper-partograph) associated with lower rate of...?			
From the Register Analysis			
Neonatal deaths <24 hours and (Tool 5)	Number of early neonatal deaths. This is a count variable.	All live births	We will compare means using t-tests across 2 groups. Next, we will use unadjusted regression models that account for clustering (correlation) of data within the facility. Poisson regression with offset term (or another appropriate model to be explored) will be used for bivariate and multivariable analysis.

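### The assignment section calls the study cluster-randomized although Section III describes purposive, non-randomised allocation; Table 5's live-birth case set excludes the stillbirths it counts, and S1 could use baseline data already scanned

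*Combined protocol and SAP*

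**What the plan says.** **Allocation.** Section III.A opens its overview thus: "The study design is a quasi-experimental design evaluation with labor management outcomes compared for the study period between two study groups, intervention and control". Phases item 2: "Within each region, equal numbers of facilities that will be purposively assigned to the study groups". Item 2a: "Kisumu District Hospital and Meru Teaching and Referral Hospital must be intervention sites and will not be randomly allocated to the study group". Section V.C.6.a, which answers how arms are assigned: "This will be a cluster-randomized trial. See section on randomization under Section III Methods". The analysis text that follows Table 5 opens its confounding paragraph with "While we have selected clinics roughly matched between the intervention and comparison regions".

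**S1 analysis (Table 5 and the text after it).** Neonatal deaths, fresh stillbirths and their sum are compared first by t-test and then by regression that accounts for facility clustering. On the model: "Poisson regression with offset term (or another appropriate model to be explored) will be used for bivariate and multivariable analysis". On covariates: "Facility level possible confounders are: monthly case load of laboring women, number of providers, key equipment availability etc". No baseline event rate is named.

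**S1 case set and outcome.** Table 5 gives live births as the case set for all three outcomes. The row label for neonatal deaths limits them to under 24 hours, while the outcome cell of the same row counts early neonatal deaths without that limit.

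**Baseline data.** Section X.D has study staff, or a designated provider on site, "scan registers for the three previous months to establish the baseline rate for maternal and early newborn deaths and fresh stillbirths". The only stated use is a safety trigger, when events run more than 10% above the prior average.

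**The concern.** Allocation is the first thing a reader needs in order to judge whether a difference between arms can be read causally, and Section I says the results will inform the Ministry of Health on wider use. Someone who reads only Section V.C.6.a would take the results as randomised evidence.

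The case set matters because a stillborn baby is not a live birth. As written, the population at risk excludes the events in the numerator.

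The baseline question arises because purposive allocation balances the arms on birth volume, staffing and emergency obstetric care level only as far as possible. Mortality is not on that list. A stable mortality gap that existed before the study could therefore enter the S1 comparison, and the data that would help to address it are already to be collected.

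**Working it through.** **1. Allocation, passages side by side.**

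| Place | Description |
|---|---|
| III.A Study Design | quasi-experimental |
| III.A Phases item 2 | purposive, equal numbers within each region |
| III.A Phases item 2a | two named hospitals fixed to ePartogram |
| V.C.6.a | cluster-randomized, with a cross-reference |
| Analysis text after Table 5 | matched between intervention and comparison regions |

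The text of Section III has no randomization section and no randomization procedure. Figure 1 is not shown, but a figure could not reconcile purposive with randomized assignment. The word regions in the last row is loose, since item 2 assigns facilities to both groups within each region.

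**2. Does a stated figure depend on the label?** The plan's calculated figure is 2,009 partographs for P3 (Section III.B, Table 1). Two-sided 5% and 80% power are not stated; they are inferred because they return the table.
- Cluster size = 671 × 0.80 × 0.19 / 6 = 17.0.
- Design effect = 1 + (17.0 − 1) × (1 + 0.90²) × 0.15 = 5.34 (stated 5.3).
- Unadjusted n = 7.849 × (0.50 × 0.50 + 0.80 × 0.20) / 0.30² = 35.8 (stated 36).
- 35.8 × 5.34 = 191; 191 / 0.19 ≈ 1,006 per arm; total about 2,011 (stated 2,009).

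The figure reproduces, and nothing in it depends on how facilities were allocated.

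**3. Stillbirth denominator.** Assume fresh-stillbirth risks of 3% and 2% of live births plus fresh stillbirths; the documents give none. The correct ratio is 0.03/0.02 = 1.500. Dividing by live births only gives (0.03/0.97)/(0.02/0.98) = 1.515, about 1% too high.

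**4. Baseline adjustment, illustration only.** From the documents: 671 births per month per arm, 6 facilities per arm, coefficient of variation of volume 0.9, three baseline months. Assumed: 10-30 events per 1,000 births, three study months, between-facility SD of the log rate (tau) of 0, 0.3 or 0.5, no facility-by-period variation, no true effect, and a pre-existing log-rate gap of 0.20 (rate ratio exp(0.20) = 1.22).

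Baseline events per facility = 671 × 3 / 6 × rate = 335.5 × rate, so about 3, 7 and 10 at 10, 20 and 30 per 1,000. With volumes this unequal, about 2.3, 1.1 and 0.7 of the 12 facilities are expected to have none.

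Simulation with 20,000 runs per cell, mean (SD) of the estimated log rate ratio. The adjusted model is Poisson with a log-births offset, arm and a shrunken log baseline rate; the comparator has arm only.

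| Rate per 1,000 | tau | Arm only | Adjusted | SD change |
|---|---|---|---|---|
| 10 | 0 | 0.21 (0.315) | 0.21 (0.351) | +11% |
| 10 | 0.3 | 0.21 (0.385) | 0.15 (0.398) | +3% |
| 10 | 0.5 | 0.21 (0.490) | 0.10 (0.424) | −13% |
| 20 | 0 | 0.21 (0.216) | 0.20 (0.247) | +14% |
| 20 | 0.3 | 0.20 (0.308) | 0.12 (0.294) | −5% |
| 20 | 0.5 | 0.21 (0.431) | 0.07 (0.310) | −28% |
| 30 | 0 | 0.20 (0.175) | 0.20 (0.202) | +15% |
| 30 | 0.3 | 0.20 (0.282) | 0.10 (0.248) | −12% |
| 30 | 0.5 | 0.20 (0.413) | 0.05 (0.260) | −37% |

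Adjustment removes little or none of the gap when facilities do not otherwise differ, and more as they differ more. The exact values depend on how the baseline rate is shrunk.

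**5. Degrees of freedom with 12 facilities.** Arm only: 10 to 9, critical t 2.228 to 2.262 (+1.5%). With the three facility covariates the plan names: 7 to 6, 2.365 to 2.447 (+3.5%).

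**The case against.** The label sits in one form answer that defers to Section III, and Section III is clear. The analysis text speaks of rough matching and plans to evaluate confounding, and S1 is worded as an association. All of this stands: correcting the label alters no sample size and no planned model. It does not remove the contradiction, because both statements are current text and V.C.6.a is the place where a reader looks for the allocation method.

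On S1, the plan does not exclude a baseline term. Its covariate list is open-ended and it allows another model. The register scan is written as a safety procedure, so no promise to use it in the analysis is broken. The outcome is secondary. The illustration rests on assumed rates, SDs and gap, and its comparator omits the covariates the plan names, which could absorb part of a gap. These points stand too, and they make the baseline term an improvement rather than a correction.

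Stronger readings that a reader might infer are not supported:
- That S1 ignores confounding, or would carry the whole of a pre-existing gap. Multivariable adjustment is planned.
- That arm and region coincide. Section III.A assigns within region.
- That the two fixed hospitals call for an analysis that drops them with their control counterparts. No counterparts are named, and under purposive assignment these hospitals are no less randomised than the others.

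**Conclusion.** Two points are wrong as written. The design label in V.C.6.a and its cross-reference contradict Section III.A; the consequence is for interpretation, with no change in any figure. The live-birth case set for fresh stillbirths and combined events excludes events being counted; the effect is about 1% on a ratio at assumed risks of 3% and 2%. The two definitions of neonatal death inside Table 5 also need to be reconciled.

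The third point is a cheap improvement and not an error. S1 names no baseline event rate although three prior months of registers will be in hand. How much an adjustment would help depends on between-facility variation that the documents do not give, so the simulated figures show direction and trade-off only.

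**What to change.** **Allocation.** In V.C.6.a, describe allocation as non-randomised and purposive. If any other sites are in fact randomised, say which and how. Delete the cross-reference, change regions to groups in the confounding paragraph, and word conclusions as associations. Cost: wording only.

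**Table 5.** For fresh stillbirths and combined events, use live births plus fresh stillbirths, or total births with macerated stillbirths stated as included. The Register Review Tool (Table 4, Tool 5) records all of these. Settle on one neonatal-death definition for the row label, the outcome cell and the baseline months.

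**S1.** Before any modelling of outcomes by arm, prespecify an analysis adjusted for each facility's event rate in the three prior months, define any shrinkage, give a rule for facilities with no baseline events, and report it beside the plan's own model. The time point is set this way because Section X.D already has the team reviewing event rates every two weeks. Costs:
- abstraction of registers already to be scanned;
- only partial adjustment, since the baseline rate is noisy;
- about 11-15% more standard error if facilities do not differ;
- one degree of freedom (+1.5% in the critical t value with arm only, +3.5% with the three named covariates);
- possible changes in recording after the register training (Phases item 4b), which the baseline months predate.
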